## 18 Appendices

### 18.1 CTCAE Immune System Hypersensitivity Grades

Adverse Event	Grade 1	Grade 2	Grade 3	Grade 4	Grade 5
Allergic reaction	Transient flushing or rash, drug fever <38°C (<100.4°F); intervention not indicated	Intervention or infusion interruption indicated; responds promptly to symptomatic treatment (e.g., antihistamines, NSAIDS, narcotics); prophylactic medications indicated for ≤24 hours	Prolonged (e.g., not rapidly responsive to symptomatic medication and/or brief interruption of infusion); recurrence of symptoms following initial improvement; hospitalization indicated for clinical sequelae (e.g., renal impairment, pulmonary infiltrates)	Life-threatening consequences; urgent intervention indicated	Death
Allergic reaction = A disorder characterized by an adverse local or general response from exposure to an allergen.					
Anaphylaxis	-	-	Symptomatic bronchospasm, with or without urticaria; parenteral intervention indicated; allergy-related edema/angioedema ; hypotension	Life-threatening consequences; urgent intervention indicated	Death
Anaphylaxis = A disorder characterized by an acute inflammatory reaction resulting from the release of histamine and histamine-like substances from mast cells, causing a hypersensitivity immune response. Clinically, it presents with breathing difficulty, dizziness, hypotension, cyanosis, and loss of consciousness and may lead to death.					
Autoimmune disorder	Asymptomatic; serologic or other evidence of autoimmune reaction, with normal organ function; intervention not indicated	Evidence of autoimmune reaction involving a non-essential organ or function (e.g., hypothyroidism)	Autoimmune reactions involving major organ (e.g., colitis, anemia, myocarditis, kidney)	Life-threatening consequences; urgent intervention indicated	Death
Autoimmune disorder = A disorder resulting from loss of function or tissue destruction of an organ or multiple organs, arising from humoral or cellular immune responses of the individual to his own tissue constituents.					

Adverse Event	Grade 1	Grade 2	Grade 3	Grade 4	Grade 5
Cytokine release syndrome	Mild reaction; infusion interruption not indicated; intervention not indicated	Therapy or infusion interruption indicated but responds promptly to symptomatic treatment (e.g., antihistamines, NSAIDS, narcotics, intravenous fluids); prophylactic medications indicated for ≤24 hours	Prolonged (e.g., not rapidly responsive to symptomatic medication and/or brief interruption of infusion); recurrence of symptoms following initial improvement; hospitalization indicated for clinical sequelae (e.g., renal impairment, pulmonary infiltrates)	Life-threatening consequences; pressor or ventilatory support indicated	Death
Cytokine release syndrome = A disorder characterized by nausea, headache, tachycardia, hypotension, rash, and shortness of breath; it is caused by the release of cytokines from the cells.					
Serum sickness	Asymptomatic; clinical or diagnostic observations only; intervention not indicated	Moderate arthralgia; fever, rash, urticaria, antihistamines indicated	Severe arthralgia or arthritis; extensive rash; steroids or intravenous fluids indicated	Life-threatening consequences; pressor or ventilatory support indicated	Death
Serum sickness = A disorder characterized by a delayed-type hypersensitivity reaction to foreign proteins derived from an animal serum. It occurs approximately 6 to 21 days following the administration of the foreign antigen. Symptoms include fever, arthralgias, myalgias, skin eruptions, lymphadenopathy, chest marked discomfort, and dyspnea.					
Immune system disorders - Other, specify	Asymptomatic or mild symptoms; clinical or diagnostic observations only; intervention not indicated	Moderate; minimal, local or noninvasive intervention indicated; limiting age-appropriate instrumental ADL	Severe or medically significant but not immediately life-threatening; hospitalization or prolongation of existing hospitalization indicated; disabling; limiting self-care ADL	Life-threatening consequences; urgent intervention indicated	Death

ADL = Activities of daily living; NSAIDs = non-steroidal anti-inflammatory drugs.

Adapted from CTCAE version 4.0 – June 14, 2010, Immune system disorders.

## 18.2 Eastern Cooperative Oncology Group Performance Status

Performance status will be assessed using the ECOG performance status grades as indicated below:

Grade	Definition
0	Fully active, able to carry on all predisease performance without restriction.
1	Restricted in physically strenuous activity but ambulatory and able to carry out work of a light or sedentary nature (e.g., light house work, office work).
2	Ambulatory and capable of all self-care but unable to carry out any work activities. Up and about more than 50% of waking hours.
3	Capable of only limited self-care, confined to bed or chair more than 50% of waking hours.
4	Completely disabled. Cannot carry on any self-care. Totally confined to bed or chair.
5	Dead.
Oken, 1982	

## 18.3 Somatic Mutations Observed via Next Generation Sequencing

[Table 5](#) lists somatic *ERBB2/HER2* mutations obtained from the cbiportal database (<http://www.cbiportal.org>, accessed 20 December 2016), which were identified as recurrent hotspots (statistically significant) in a population-scale cohort of tumor samples of various cancer types using methodology based on [Chang, 2016](#).

**Table 5: List of Somatic *ERBB2/HER2* Mutations Obtained from the Cbiportal Database**

Amino Acid Position	Mutation Type
L755M	Single Residue Change
L755P	Single Residue Change
L755S	Single Residue Change
L755W	Single Residue Change
S310F	Single Residue Change
S310Y	Single Residue Change
V777L	Single Residue Change
V777M	Single Residue Change
V842I	Single Residue Change
D769H	Single Residue Change
D769N	Single Residue Change
D769Y	Single Residue Change
R678Q	Single Residue Change

Additional *ERBB2/HER2* mutations, which are known to be oncogenic based in part on [Bose, 2013](#); [Hyman, 2016](#); and [Gonzalvez, 2016](#), are listed below in [Table 6](#).

**Table 6: List of *ERBB2/HER2* Mutations Known to be Oncogenic**

Amino Acid Position	Mutation Type
G309A	Single Residue Change
G309E	Single Residue Change
V842I	Single Residue Change
R896C	Single Residue Change
Y772_V773insRDGE	Insertion
Y772_A775dup synonymous 772-775, in-frame indel	Duplication
G778_S779insLPS	In frame insertion
P780-Y781insGSP synonymous G778_p780dup	In frame Insertion
L869R	Single Residue Change

Most of the *HER2* mutations observed in lung cancer to date have been insertions within a small stretch of exon 20 on the *ERBB2/HER2* gene. Such aberrations are likely oncogenic and are displayed in [Table 7](#) ([Mazieres, 2013](#); [Buttitta, 2006](#); [Shigematsu, 2005](#)).

**Table 7: Insertional *HER2* Mutations Predominantly Identified in Lung Cancer**

Amino Acid Position	Mutation Type
G776_777insVC synonymous G776>VC synonymous G776delinsVC	In frame insertion
A775 or G776	Any in frame insertion/duplication at this position, including but not limited to A775_G776insYVMA e.g. 776–779 (YVMA) qualifies as well
GSP 781-783 ins	In frame insertion
G776V	In frame codon insertion
G776L	In frame codon insertion

It is plausible to assume that all listed mutations are likely to have a tumor promoting impact on the *HER2* protein, and that tumor cells therefore express such altered protein in order to gain a growth and/or survival advantage over neighboring cells.

Moreover, *HER2* hotspot mutations are a good predictor for functional relevance ([Bose, 2013](#)), and hence all mutations listed in this section including the ones from cbiportal listed in [Table 8](#) qualify for participation in Part 1 of the study. Additionally, patients with mutations that are reported with variation in terminology on the corresponding NGS report, but that have the same meaning as those listed here, will be permitted into the study.

**Table 8: List of Mutations from Cbioportal**

Amino Acid Position	Mutation Type
G776S	Single Residue Change
G660D	Single Residue Change
G660R	Single Residue Change
T733I	Single Residue Change
T862A	Single Residue Change
T862S	Single Residue Change

## 18.4 Appendix: Modified Continual Reassessment Method of Dose Escalation

### 18.4.1 Overview

Planned dose levels for ADCT-502 are shown below in [Table 9](#). Dose escalation will be conducted according to a mCRM, with dose EWOC and no dose skipping.

A recommendation to escalate, stay, or deescalate the dose level for the next 2 patient cohorts will be made according to the planned dose scheme in [Table 9](#).

The study will be continuously monitored for safety and early stopping for successfully identifying the MTD. Dose escalation will be stopped when 3 cohorts are consecutively assigned to the same dose level, which will be identified as the MTD.

**Table 9: Planned Dose Levels for ADCT-502**

Dose Level	Dose of ADCT-502	Dose Level	Dose of ADCT-502
1	30 µg/kg	7	240 µg/kg
2	60 µg/kg	8	300 µg/kg
3	120 µg/kg	9	350 µg/kg
4	150 µg/kg	10	400 µg/kg
5	180 µg/kg	11	450 µg/kg
6	210 µg/kg	12	500 µg/kg

### 18.4.2 Model and Priors

Dose escalation in this study will be conducted using the mCRM.

For each dose,  $d = 1, \dots, n$ , we model the binary outcome of non-DLT, or a DLT.

The log odds of a DLT are modeled as

$$\theta_d = \log\left(\frac{\pi_{DLT}}{1 - \pi_{DLT}}\right)$$

with a 2-parameter model

$$\theta_d = \alpha + \exp(\beta) \log(d_i / d^*)$$

where  $d^*$  is the reference dose, which is used to standardize the dose  $d_i$  and allows for the interpretation of  $\alpha$  as the odds of a DLT at  $d^*$ .  $\exp(\beta)$  is positive, ensuring a monotonically increasing dose-toxicity relationship.

[Neuenschwander, 2008](#) placed a bivariate lognormal prior on the two parameters and proposed eliciting information on the risk of DLT at two (2) or more doses to obtain prior means and variances. Several articles have examined the specification of priors. When there are no previous historical clinical data available, it is possible to use uninformative prior. For this purpose, the above model can be re-parametrized in terms of  $(\rho_0, \gamma)$ , where  $\rho_0$  is the probability of a DLT at the starting dose  $d_1$  and  $\gamma$  is the MTD, the dose expected to produce DLT at 0.3 probability in this study, with

$$\gamma = \exp(-\beta) * (\log(\theta_d) - \log(1 - \theta_d) - \alpha)$$

and placing the following independent prior distributions on the parameters.

$$\rho_0 \sim \text{Uniform}(0, 0.30)$$

$$\gamma \sim \text{Uniform}(d_1, d_n).$$

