#### **4.6 Description of Dose Escalation Process**

Each cohort will consist of 2 patients. There will be a 24-hour observation before enrolling the second patient at Dose Level 1. The DLT observation period at each dose level is 1 cycle (3 weeks), after which it will be determined whether to escalate to the next dose level, stay at the current dose level, or de-escalate to the previous dose level for the next cohort.

There will be no de-escalation from Dose Level 1. Intrapatient dose escalation is not permitted.

Dose escalation is not permitted unless two or more patients have complete DLT information through the first cycle in any given dose level. Dose escalation will be determined by using a mCRM with a target DLT rate of 30% and an equivalence interval of 20% to 35%, and with dose escalation-with-overdose-control (EWOC) and no dose skipping.

The mCRM will be implemented in Part 1 under the oversight of a Dose Escalation Steering Committee (DESC). The DESC will confirm each escalating dose level after reviewing all available safety data. PK data from patients in that dose level and prior dose levels may also inform decision making. The DESC may halt dose escalation prior to determining the MTD based on emerging PK, PD, toxicity, or response data.

Additional patients may be included at any dose level to further assess the safety and tolerability if at least 1 patient in the study has achieved a partial response or better, or if further evaluation of PK or PD data is deemed necessary by the DESC to determine the RDE.

Furthermore, to better understand the potential efficacy of ADCT-502 in an indication approved for treatment with HER2 targeted antibodies, up to 3 additional breast cancer patients who have previously been treated with an approved HER2 targeted therapy may be enrolled per cohort at given dose levels  $\geq 60 \mu\text{g/kg}$  determined by the mCRM model to be safe.

Dose escalation will be stopped after the mCRM has assigned 3 cohorts consecutively to the same dose level.

If the MTD is not reached, the recommended dose(s) and schedule(s) for expansion (RDE) will be determined.

Once the Part 2 RDE(s) is/are determined, patients receiving lower or higher dose levels of ADCT-502 enrolled in part 1 may be offered continued treatment at the RDE(s).

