### 12.1 Sample Size Calculations

**Part 1:** The number of patients will depend upon the toxicities observed, the number of dose-level cohorts evaluated, and the number of dose-level cohorts expanded as the study progresses; approximately 30 patients are estimated. Overall sample size will be guided by the mCRM design.

**Part 2:** During the dose expansion phase of the study, up to 28 patients per each dose expansion cohort will be enrolled. Simon's two-stage design ([Simon, 1989](#)) will be used. The null hypothesis that the true response rate is 7.5% will be tested against a one-sided alternative. In the first stage, 13 patients will be accrued. If there are one (1) or fewer responses in these 13 patients, the cohort will be closed. Otherwise, 15 additional patients will be accrued for a total of 28 patients. The null hypothesis will be rejected if five (5) or more responses are observed in 28 patients. This design yields a type I error rate of 0.05 (one-sided) and power of 80% when the true response rate is 25%.

In the basket group, up to 24 patients will be enrolled, with no more than 3 patients from each indication. If responses are observed, plans are described in [Section 12.2](#) (Interim Analysis [Part 2]).

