### **18.4.3.1 Stopping Rules**

Patients will continue to be recruited into the study until 3 cohorts of patients are consecutively assigned to the same dose level, which will be identified as the MTD.

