### **18.4.4 Interim Monitoring**

The study will be continuously monitored for safety and for success in identifying the MTD. If dose escalation is not stopped for either safety or success in identifying the MTD, it will continue to enroll to the maximum sample size.

[figure not shown]

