#### **18.4.4.1 Safety Monitoring**

[figure not shown]
The lowest dose (the initial starting dose) will be considered unsafe if the probability of excessive or unacceptable toxicity is  $> 25\%$ . The trial will stop, and no MTD found, if the lowest dose is considered unsafe (hence all doses are considered unsafe).

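### Appendix 18.4: the gamma formula does not solve its own model, and the three-cohort rule labels a dose the MTD even when no DLT has occurred

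*Protocol*

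**What the plan says.** Protocol Section 18.4.2 defines theta_d as the log odds of a DLT and prints one model: theta_d = alpha + exp(beta) x log(d/d*). It calls alpha the odds at d*. It then reparametrises to rho_0 (the DLT probability at the starting dose) and gamma, which "is the MTD, the dose expected to produce DLT at 0.3 probability in this study", with gamma = exp(-beta) x (log(theta_d) - log(1 - theta_d) - alpha). The priors are rho_0 ~ Uniform(0, 0.30) and gamma ~ Uniform(d_1, d_n), introduced as uninformative. From Table 9, d_1 = 30 and d_n = 500 µg/kg. Section 18.4.3 uses theta_d again, this time for intervals between 0 and 1.

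On the label, Section 18.4.1 states: "Dose escalation will be stopped when 3 cohorts are consecutively assigned to the same dose level, which will be identified as the MTD". Section 18.4.3.1 repeats the rule. Section 4.6 gives the same stop without the label and then continues: "If the MTD is not reached", an RDE is to be determined.

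Other endings are also described:
- Section 4.6: "The DESC may halt dose escalation prior to determining the MTD based on emerging PK, PD, toxicity, or response data".
- Section 18.4.4, when neither safety nor success stops escalation: "it will continue to enroll to the maximum sample size". No number is given. Section 12.1 says only that "approximately 30 patients are estimated".
- Section 18.4.4.1: "The trial will stop, and no MTD found, if the lowest dose is considered unsafe".
- Section 2.4 allows a switch to a 3+3 design if the dosing interval changes or an intermediate dose is used.

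**The concern.** Two things look wrong. First, a programmer who works from Section 18.4.2 cannot obtain the MTD parameter from the formula given, and one symbol stands for two quantities. Second, the Appendix gives the MTD two meanings: the dose with a 30% DLT probability, and the dose at which three cohorts in a row were treated. The two can differ most when toxicity is low, which is the case that Section 4.6 seems meant to cover.

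Determining the MTD and/or RDE is the Part 1 primary objective (Protocol Section 3.1.1, kept in SAP Section 2.1). At stake is whether a reported MTD rests on observed toxicity or only on a stopping rule combined with a prior.

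**Working it through.** **1. The formula.** Set the DLT probability to 0.30 in the printed model. With logit(0.30) = log(0.30/0.70) = -0.847:

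log(gamma/d*) = exp(-beta) x [logit(0.30) - alpha], so gamma = d* x exp{exp(-beta) x [logit(0.30) - alpha]}.

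The printed expression can be read in two ways.
- theta_d as defined, a log odds: at the target theta_d = -0.847, and log(theta_d) does not exist.
- theta_d = 0.30: the expression equals log(gamma/d*), which is not a dose.

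Illustration with assumed values alpha = logit(0.15) = -1.735, beta = 0, d* = 120 µg/kg (the documents give no d*):
- Printed formula: -0.847 + 1.735 = 0.887.
- Model: 120 x exp(0.887) = 291.4 µg/kg.
- A dose of 0.887 µg/kg put back into the model has DLT odds of (0.15/0.85) x 0.887/120 = 0.0013, so a probability of about 0.001 and not 0.30. The value also lies outside (30, 500).

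**2. The DLT-free path.** In terms of rho_0 and gamma, d* cancels:

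logit p(d) = logit(rho_0) + [logit(0.30) - logit(rho_0)] x log(d/30)/log(gamma/30).

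Inputs: the printed priors, the 12 doses of Table 9, cohorts of 2 (Section 4.6), the dose that maximises P(0.20 to 0.35) among doses with P(>0.35) at most 25% (Section 18.4.3), no skipping, and a stop after the third consecutive cohort at one dose. With a grid posterior and no DLTs, the cohorts go to 30, 60, 120, 150, 180, 210, 240, 300, 350, 350 and 350 µg/kg. That is 11 cohorts, 22 patients, and 350 µg/kg is labelled the MTD with 0/6 DLTs at that dose and 0/22 overall.

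At that moment P(0.20 to 0.35) is about 0.89 at 350 and 0.90 at 400, and P(>0.35) at 400 is 0.097. The design's own rule would therefore choose 400 next. The margin is small, and this preference does not carry over to the larger cohorts below that were checked for it.

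**3. Cohort size.** Section 18.4.3 allows larger cohorts, and Section 4.6 allows up to 3 extra breast cancer patients per cohort from 60 µg/kg. DLT-free end points under the printed model:

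| Cohorts | Labelled MTD | DLTs |
|---|---|---|
| 2 | 350 µg/kg | 0/22 |
| 2, plus 1 extra from 60 µg/kg | 400 µg/kg | 0/35 |
| 3 | 400 µg/kg | 0/36 |
| 4 | 400 µg/kg | 0/48 |
| 5 | 450 µg/kg (400 on a coarser grid) | 0/70 |

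If the misprinted formula were programmed as a model linear in dose, cohorts of 2 would end at 400 µg/kg after 0/24. An MTD is declared in every case. If the unstated maximum were 30 patients (an assumption), it would not intervene with cohorts of 2, which end at 22, but would with cohorts of 3, which end at 36.

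**4. Why the path stalls.** Every prior value of gamma is at most 500, so p(500) is at least 0.30 whatever the data. After 0/22 the posterior mean DLT rate is still about 27% at 350 and 35% at 500. With assumed upper bounds of 600, 650 and 750 µg/kg the path ends at 450, 500 and 500, and P(gamma > 500) is 0.59, 0.79 and 0.88. The dose is still labelled the MTD, so the label problem is separate from the prior.

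**5. How often.** The chance that the label comes with no DLT in the whole of Part 1, cohorts of 2:
- Assumed flat 2% rate: 0.98^22 = 0.641.
- Assumed flat 5% rate: 0.95^22 = 0.324.
- Protocol Scenario 3: (0.98 x 0.96 x 0.94 x 0.93 x 0.92 x 0.91 x 0.895 x 0.875)^2 x 0.835^6 = 0.0985.

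These shares fall as cohorts grow. With one extra patient per cohort from 60 µg/kg, the 2% figure is 0.98^35 = 0.493. With three extra it is about 35% or less.

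**The case against.** Section 4.6 and the Appendix are not flatly incompatible. A DESC halt, the maximum sample size and the 3+3 switch can each end Part 1 without an MTD, so the provision in Section 4.6 is not empty. This stands. None of those routes, however, says what a three-cohort stop without toxicity means, and the Appendix answers that with an unconditional label.

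Several stronger readings are tempting, and the documents do not support them.
- *The text permits two models.* Only one is printed, in log(d/d*). The linear version arises only if a faulty derived expression is allowed to override the model equation.
- *The target interval means DLT rates of 55% to 59%.* That follows only if theta_d in Section 18.4.3 is read as a log odds. The intervals there run up to 1, and Section 4.6 states a 20% to 35% DLT rate. This is reused notation.
- *The gamma prior is wrong.* Its support is the planned dose range, and Section 2.4 makes 500 µg/kg the highest dose to be tested. Widening is a trade-off: with an assumed bound of 600 and cohorts of 2, Scenario 4 selection of doses with a true rate above 0.35 rises from 18% to 30%. The prior needs an accurate description, because a hard bound is not uninformative.
- *The design never finds an acceptable dose in Scenario 3.* In-band selection was 0 of 2,000 simulated trials with bare cohorts of 2. It is about 14% with one extra patient per cohort from 60 µg/kg and up to about 34% with three.
- *Patients would be overdosed.* In the Scenario 3 runs with cohorts of 2, no labelled dose had a true rate above 0.35. The errors there are on the low side.

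**Conclusion.** The point holds in two parts. The gamma expression in Section 18.4.2 is wrong as printed, by algebra and without any assumption. The MTD label in Sections 18.4.1 and 18.4.3.1 has no toxicity condition, does not match the definition in Section 18.4.2, and is not reconciled with Section 4.6. Under the printed model and prior, a DLT-free Part 1 with cohorts of 2 yields an MTD of 350 µg/kg after 0/22. Other permitted cohort sizes yield other doses, still with no DLT.

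The dose figures rest on a re-implementation from the text. The sponsor's operating-characteristic figures are not shown and its software may differ. The flat DLT rates are assumptions.

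The consequence is a wrong MTD label and a model that cannot be reproduced from the text. It is limited further because the SAP reports early termination with Part 2 not performed (Section 3.3), only lists DLTs (Section 4.8.1) and gives no MTD analysis. The effect is on any MTD statement in the report. This should be fixed, but it does not put the conduct of dose escalation in doubt.

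**What to change.** 1. In Section 18.4.2 print gamma = d* x exp{exp(-beta) x [logit(0.30) - alpha]}. Use separate symbols for the log odds and the DLT probability here and in Section 18.4.3, and call alpha the log odds. Describe the gamma prior as bounded at the highest planned dose and drop the word uninformative.
2. Reconcile Sections 18.4.1 and 18.4.3.1 with Section 4.6 by a pre-stated reporting criterion, so that a three-cohort stop with no or almost no toxicity is reported as MTD not reached, with an RDE. The sponsor chooses the criterion and checks it by simulation at the cohort sizes the protocol allows, with a no-toxicity scenario added. A fixed DLT count is a weak choice: withholding the label at zero DLTs catches 64% of trials at an assumed flat 2% rate with cohorts of 2, but only about 49% to 35% or less with one to three extra patients per cohort. A criterion on P(gamma > 500) cannot work under the present prior, where that probability is always zero.
3. State the maximum sample size to which Section 18.4.4 refers.

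The cost is appendix wording, one reporting rule and a simulation re-run. Dose assignment and the choice of RDE do not change, and no dose, prior bound or threshold is proposed here. Since Part 1 has ended, a criterion added now is post hoc, and the report should say so beside any MTD statement.
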